4.4 Analysis of Efficacy

4.4.1 Primary Efficacy Endpoint

4.4.1.1 Primary Efficacy Endpoint Definition

The primary efficacy variable is the change from baseline in overall MLSI score. The primary time-point is 8 weeks. The overall MLSI (A×I) for each subject is derived at a tooth site level first before averaging over all the non-missing teeth sites assessed. The change from baseline is derived from the individual sites first before calculating the average change across the sites assessed.

4.4.1.2 Statistical Hypothesis, Model, and Method of Analysis

The primary objective is to evaluate the ranking order in extrinsic dental stain removal, as measured by overall MLSI (A×I), of a 0.5% spherical silica dentifrice, a marketed 6% abrasive silica dentifrice, a 1% spherical silica / 5% STP dentifrice, and a marketed 16% abrasive silica / 5% STP dentifrice, after 8 weeks twice daily brushing.

Summary statistics including mean, SD, median, min, max will be provided for baseline and Week 8 by randomized treatment group ([Table 14.2.2.1](#)). The change from baseline in overall MLSI will be analyzed using analysis of covariance (ANCOVA) with treatment as a fixed effect and baseline overall MLSI as a covariate.

| | | | | |
|---|------------------|--|---------------------|----------------|
|  GlaxoSmithKline | Document Name | gsk-208078-reporting-and-analysis-plan.pdf | | |
| | Type | Version | Document Identifier | Effective Date |
| | elido_controlled | 0.1, CURRENT; Most-Recent; In Review | 090032d580f4eeeb | |
| | Reason For Issue | | | |

Potassium Nitrate / Sodium Fluoride

208078

Final Statistical Reporting and Analysis plan Amendment 21NOV2017

There are no comparisons for the primary objective as the main objective is to look at the rank order of the treatments in level of stain reduction after 8 weeks of treatment. This will be achieved via the adjusted means and confidence intervals (Cis) for the means along with plots of MLSI over time. Adjusted means of all treatments will be provided together with their 95% Cis and p-values ([Table 14.2.2.2](#)).

The assumption of normality and homogeneity of variance in the ANCOVA model will be investigated. Violation of this assumption will be overcome using a suitable data transformation or a non-parametric technique (e.g. Wilcoxon Rank Sum test).

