
 To evaluate the ranking order in extrinsic dental stain removal, as measured by overall MLSI Area (A), of a 0.5% spherical silica dentifrice, a marketed 6% abrasive silica dentifrice, a 1% spherical silica / 5% STP dentifrice, and a marketed 16% abrasive silica / 5% STP dentifrice, after 2, 4 and 8 weeks twice daily brushing. 	
 Change from baseline in overall MLSI Area at 2, 4 and 8 weeks.

 To evaluate the ranking order in extrinsic dental stain removal, as measured by overall MLSI Intensity (I), of a low abrasivity 0.5% spherical silica dentifrice, a marketed low abrasivity dentifrice, a moderate abrasivity 1% spherical silica / 5% STP dentifrice, and a marketed higher 	
 Change from baseline in overall MLSI Intensity at 2, 4 and 8 weeks.

GlaxoSmithKline Consumer Healthcare Confidential

Template Version Effective: 22-Jun-2017

Page 19 of 61

Document Name	003270876tprotocol.pdf	Document Identifier	Effective Date
Type	Version		
eldo_clinicalelbc	0.0. DIFFERENT MESSAGING CURRENT	1090032d580fb904bc	14-Aug-2017 09:06:22

Potassium Nitrate / Sodium Fluoride

208078

Final 1.0 Clinical Protocol

abrasivity 5% STP whitening dentifrice, after 2, 4 and 8 weeks twice daily brushing.	
Safety	

 To evaluate the safety and oral tolerability of the test dentifrices when used twice daily for 8 weeks. 	
 Adverse Events

This is a POP study designed to look at the relative extrinsic dental stain and plaque removal performance for all test dentifrices. However, we would expect the following rank order in overall MLSI (A×I) to be observed: the 1% spherical silica / 5% STP dentifrice \geq 16% abrasive silica / 5% STP dentifrice \geq 0.5% spherical silica dentifrice \geq 6% abrasive silica dentifrice.

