10.2 Statistical Methods and Analytical Plan

Additional details of the proposed statistical analysis will be documented in the statistical analysis plan (SAP), which will be written following finalization of the protocol and prior to study unblinding as appropriate.

Treatment differences in the study variables will be tested with the null hypothesis:

H0: there is no treatment difference versus the alternate hypothesis

H1: there is a treatment difference.

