4.5 Analysis of Secondary Objectives

4.5.1 Efficacy

The hypothesis is that the test products will reduce stain to a similar or greater extent than the reference products.

Two comparisons of interest will be done under the secondary objectives. These comparisons are:-

Test Product 1 vs Reference Product 1

Test Product 2 vs Reference Product 2.

The change from baseline in overall MLSI at Week 8 will be analyzed using ANCOVA with treatment as a fixed effect and baseline overall MLSI as a covariate.

From the above ANCOVA model, treatment differences between groups (Test Product 1 vs Reference Product 1 and Test Product 2 vs Reference Product 2), 95% Cis and p-values, will be provided ([Table 14.2.2.2](#)).

The assumption of normality and homogeneity of variance in the ANCOVA model will be investigated. Violation of this assumption will be overcome using a suitable data transformation or a non-parametric technique (e.g. Wilcoxon Rank Sum test).

| | | | | |
|---|------------------|--|---------------------|----------------|
|  GlaxoSmithKline | Document Name | gsk-208078-reporting-and-analysis-plan.pdf | | |
| | Type | Version | Document Identifier | Effective Date |
| | elido_controlled | 0.1, CURRENT; Most-Recent; In Review | 090032d580f4eeeb | |
| | Reason For Issue | | | |

Potassium Nitrate / Sodium Fluoride

208078

Final Statistical Reporting and Analysis plan Amendment 21NOV2017

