4.6.1.2 Analysis of Exploratory Variables

Summary statistics including mean, SD, median, min, and max will be provided for week 2 and week 4 by randomized treatment group ([Table 14.2.2.1](#)).

All stain variables will be analyzed as per the primary efficacy variable using the appropriate baseline values as a covariate.

The change from baseline in TPI variables will be analyzed using analysis of covariance (ANCOVA) with treatment and MLSI stratification as fixed effects and appropriate baseline (pre-treatment) TPI as a covariate.

From ANCOVA model, the adjusted mean for each treatment group will be provided with 95% Cis and corresponding p-values.

Results for overall interproximal MLSI (AxI) score, overall MLSI area score, overall MLSI intensity score, overall TPI score and overall Interproximal TPI Score will be presented in [Table 14.2.3.1](#), [Table 14.2.3.2](#), [Table 14.2.4.1](#), [Table 14.2.4.2](#), [Table 14.2.5.1](#), [Table 14.2.5.2](#), [Table 14.2.6.1](#), [Table 14.2.6.2](#) and [Table 14.2.7.1](#), [Table 14.2.7.2](#) respectively.

| | | | | |
|---|------------------|--|---------------------|----------------|
|  GlaxoSmithKline | Document Name | gsk-208078-reporting-and-analysis-plan.pdf | | |
| | Type | Version | Document Identifier | Effective Date |
| | elido_controlled | 0.1, CURRENT; Most-Recent; In Review | 090032d580f4eeeb | |
| | Reason For Issue | | | |

Potassium Nitrate / Sodium Fluoride

208078

Final Statistical Reporting and Analysis plan Amendment 21NOV2017

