| Reason For Issue | | | |

Potassium Nitrate / Sodium Fluoride

208078

Final Statistical Reporting and Analysis plan Amendment 21NOV2017

Protocol 208078

Program Run Date: DDMMYYYY

Table 14.2.2.2
Statistical Analysis of Overall Change Baseline in MLSI Score
Intent-to-Treat Population

Study Population: Intent-to-Treat Population (N=XX)

| Visit | Test Product 1 | Test Product 2 | Reference Product 1 | Reference Product 1 |
|--------|---------------------------------------|-----------------------|---------------------|---------------------|
| | (N=XX) | (N=XX) | (N=XX) | (N=XX) |
| WEEK 2 | ADJUSTED MEANS (SE) [1] | X.XX (X.XXX) | X.XX (X.XXX) | X.XX (X.XXX) |
| | 95 % CI [1] | (X.XX, X.XX) | (X.XX, X.XX) | (X.XX, X.XX) |
| | P-VALUE [1] | 0.XXXX | 0.XXXX | 0.XXXX |
| | COMPARISON | DIFFERENCE (SE) [1,2] | 95% CI [1] | P-VALUE [1] |
| | TEST PRODUCT 1 VS REFERENCE PRODUCT 1 | X.XX (X.XXX) | (X.XX, X.XX) | 0.XXXX |
| | TEST PRODUCT 2 VS REFERENCE PRODUCT 2 | X.XX (X.XXX) | (X.XX, X.XX) | 0.XXXX |
| WEEK 4 | SAME AS ABOVE | | | |

[1] From ANCOVA with treatment as factors and baseline overall MLSI score as a covariate

[2] Difference is first named treatment minus second named treatment such that a negative difference favours the first named treatment

Page x of y

PPD

Programming note: The same summary would be provided for the Week 8 also.

| | | | |
|------------------|--|---------------------|----------------|
| Document Name | gsk-208078-reporting-and-analysis-plan.pdf | | |
| Type | Version | Document Identifier | Effective Date |
| elido controlled | 0.1; CURRENT; Most-Recent; In Review | 090032d580f4eeeb | |
| Reason For Issue | | | |

Potassium Nitrate / Sodium Fluoride

208078

Final Statistical Reporting and Analysis plan Amendment 21NOV2017

Protocol 208078

PROGRAM RUN DATE: DDMMYYYY

Table 14.2.6.1
Summary of TPI Score
Intent-to-Treat Population

Study Population: Intent-to-Treat Population (N=XX)

| Visit | TimePoint | Test Product 1 (N=XX) | | Test Product 2 (N=XX) | | ----- | Overall (N=XX) |
|-------------------|-------------------|--------------------------|-----------------------------|--------------------------|-----------------------------|-------|-------------------|
| | | Observed Values | Change from Pre-brushing | Observed Values | Change from Pre-brushing | | |
| BASELINE | PRE- BRUSHING | N | XX | XX | XX | ----- | XX |
| | | MEAN | X.XX | X.XX | XX | ----- | X.XX |
| | | SD | X.XXX | X.XXX | XX | ----- | X.XXX |

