| | | MEDIAN | X.XX | X.XX | XX | ----- | X.XX |
| | | MINIMUM | X.XX | X.XX | XX | ----- | X.XX |
| | MAXIMUM | X.XX | X.XX | X.XX | XX | ----- | X.XX |
| POST- BRUSHING | POST- BRUSHING | N | XX | XX | XX | ----- | XX |
| | | MEAN | X.XX | X.XX | X.XX | ----- | X.XX |
| | | SD | X.XXX | X.XXX | X.XXX | ----- | X.XXX |
| | | MEDIAN | X.XX | X.XX | X.XX | ----- | X.XX |
| | | MINIMUM | X.XX | X.XX | X.XX | ----- | X.XX |
| | MAXIMUM | X.XX | X.XX | X.XX | X.XX | ----- | X.XX |
| WEEK 8 | SAME AS ABOVE | | | | | | |

Page x of y

GlaxoSmithKline Consumer Healthcare Confidential

Page 32 of 53

| | | | |
|------------------|--|---------------------|----------------|
| Document Name | gsk-208078-reporting-and-analysis-plan.pdf | | |
| Type | Version | Document Identifier | Effective Date |
| elido controlled | 0.1; CURRENT; Most-Recent; In Review | 090032d580f4eeeb | |
| Reason For Issue | | | |

Potassium Nitrate / Sodium Fluoride

208078

Final Statistical Reporting and Analysis plan Amendment 21NOV2017

PPD

GlaxoSmithKline Consumer Healthcare Confidential
Page 33 of 53

| | | | |
|------------------|--|---------------------|----------------|
| Document Name | gsk-208078-reporting-and-analysis-plan.pdf | | |
| Type | Version | Document Identifier | Effective Date |
| elido controlled | 0.1; CURRENT; Most-Recent; In Review | 090032d580f4eeeb | |
| Reason For Issue | | | |

Potassium Nitrate / Sodium Fluoride

208078

Final Statistical Reporting and Analysis plan Amendment 21NOV2017

Protocol 208078

Program Run Date: DDMMYYYY

Table 14.2.6.2
Statistical Analysis of Overall Change from Baseline (Pre-brushing) in TPI Score
Intent-to-Treat Population

Study Population: Intent-to-Treat Population (N=XX)

| Visit | Test Product 1 (N=XX) | Test Product 2 (N=XX) | Reference Product 1 (N=XX) | Reference Product 1 (N=XX) |
|------------------------|--|--|--|--|
| BASELINE POST-BRUSHING | ADJUSTED MEANS (SE)[1] 95 % CI [1] P-VALUE [1] | X.XX (X.XXX) (X.XX, X.XX) 0.XXXX | X.XX (X.XXX) (X.XX, X.XX) 0.XXXX | X.XX (X.XXX) (X.XX, X.XX) 0.XXXX |
| | COMPARISON | DIFFERENCE (SE) [1,2] | 95% CI [1] | P-VALUE [1] |
| | TEST PRODUCT 1 VS REFERENCE PRODUCT 1 | X.XX (X.XXX) | (X.XX, X.XX) | 0.XXXX |
| | TEST PRODUCT 2 VS REFERENCE PRODUCT 2 | X.XX (X.XXX) | (X.XX, X.XX) | 0.XXXX |
| WEEK 8 PRE-BRUSHING | SAME AS ABOVE | | | |
| WEEK 8 POST-BRUSHING | SAME AS ABOVE | | | |

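### The primary rank order is read from per-arm means and intervals, with no planned difference for any step between the two product pairs; Appendix 1 and several table shells also carry wrong pairs or arm labels

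*SAP*

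**What the plan says.** The current plan is the SAP Amendment of 21 November 2017 with Addendum 1 of 1 February 2018.

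- **Ranking.** SAP 4.4.1.2 and Protocol 10.2.2 state that the primary objective has no comparisons. On the ranking itself the SAP says "This will be achieved via the adjusted means and confidence intervals (Cis) for the means along with plots of MLSI over time". Addendum 1, Section 5, confirms that adjusted means will be used to rank, and adds figures of per-arm adjusted means with 95% CIs. Supportive analyses (SAP 4.4.1.3) are marked not applicable.
- **Expected order.** In Protocol Section 2, "we would expect the following rank order in overall MLSI (A×I) to be observed": Test 2 ≥ Reference 2 ≥ Test 1 ≥ Reference 1.
- **Planned differences.** SAP 4.5.1 will provide "treatment differences between groups (Test Product 1 vs Reference Product 1 and Test Product 2 vs Reference Product 2), 95% Cis and p-values". Protocol 10.2.2 and the comparison rows of the Table 14.2.2.2 and 14.2.6.2 shells name the same two pairs.
- **Per-arm p-values.** For the primary variable, "Adjusted means of all treatments will be provided together with their 95% Cis and p-values". For the exploratory variables (SAP 4.6.1.2), "From ANCOVA model, the adjusted mean for each treatment group will be provided with 95% Cis and corresponding p-values". The shell footnotes name the model but not the hypothesis. The only null in the documents is in Protocol 10.2: "H0: there is no treatment difference versus the alternate hypothesis".
- **Appendix 1 and shells.** SAP Appendix 1 gives the treatment comparisons as Test 1 vs Test 2 and Reference 1 vs Reference 2. The Table 14.2.2.2 column headings read "Test Product 1 | Test Product 2 | Reference Product 1 | Reference Product 1".

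**The concern.** A rank order is a set of statements about differences between arms. An interval around one arm's mean does not show how well a step between two arms is supported. The two planned differences each sit inside a pair, so the steps that merge two pairs into one order of four have no reported precision. A reader left with per-arm intervals may judge such a step by whether they overlap, which is a much stricter rule than the interval for the difference.

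The per-arm p-values do not fill this gap. If they test zero change, which is the natural reading but is not stated, they do not address rank. The trial has no untreated arm, so they do not isolate a product effect either. For MLSI there is a further reason: the examiner selects the four assessment teeth at the baseline visit (Protocol 6.1.2), favouring teeth that stain more (Protocol 1.2.2).

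Appendix 1 describes itself as guidance for output labels. Its pairs conflict with the analysis sections, and several shells mislabel the arms.

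**Working it through.** **Inputs.** Four arms; 120 evaluable of at least 124 randomized (SAP 1.4); 95% intervals (SAP 4.4.1.2); ANCOVA with treatment and one baseline covariate. The plan's figure reproduces: 120/4 = 30 per arm (124/4 = 31). The sample-size derivation is redacted, so no SD is available and results are in units of the residual SD.

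**1. Which steps lack a difference.** Four products give 4×3/2 = 6 pairs. Two are planned. The other four all cross the pairs: Reference 2 vs Test 1, Test 2 vs Test 1, Test 2 vs Reference 1, Reference 2 vs Reference 1. Write A for Test 1 and Reference 1, and B for Test 2 and Reference 2. The 4! = 24 possible orders split by pattern:

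- AABB or BBAA: 2×2×2 = 8 orders, one uncovered adjacent step. The protocol's expected order is here, and its uncovered step is Reference 2 vs Test 1.
- ABBA or BAAB: 8 orders, two uncovered steps.
- ABAB or BABA: 8 orders, all three steps uncovered.

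Whichever order is observed, one to three of its three adjacent steps have no planned difference.

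**2. Precision.** Residual df = 120 − 5 = 115 and t = 1.981. Arms are taken as balanced, ignoring the small term for baseline imbalance.

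- One arm: 1.981/√30 = 0.362 SD.
- A difference: 1.981×√(2/30) = 0.511 SD.
- At 25 per arm: 0.397 and 0.562. At 31 per arm: 0.356 and 0.503.

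**3. Effect of judging by overlap.** Non-overlap of two per-arm intervals needs a gap of 2×0.3616 = 0.723 SD, which is √2 = 1.41 times the 0.511 SD that a direct interval needs to exclude zero. It is equivalent to a two-sided level of about 0.006. At an assumed true gap of 0.5 SD, non-overlap occurs about 19% of the time, against 49% for the direct difference at the 5% level.

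**4. Effect of ranking on point estimates.** In a simulation with both planned pairs truly 0.5 SD apart (assumed) and Reference 2 equal to Test 1, the full expected order still appeared about 45% of the time. No planned statistic would show the middle step as unsupported.

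**5. Can the reader recover it?** Closely. Combining two per-arm SEs gives √(1/30 + 1/30) = 0.258 SD, so the half-width is 1.981×0.258 = 0.511. In simulated ANCOVAs at 30 per arm, the ratio of the combined SE to the exact SE of the difference had a central 95% range of 0.990 to 1.004, and 0.997 to 1.002 with two strata of 15 per arm.

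**6. Per-arm p-values.** Four MLSI variables (overall, interproximal, area, intensity) × 3 visits = 12 analyses. Two TPI variables × 3 time points = 6. Then 18 × 4 arms = 72 p-values without a stated null: 48 for MLSI and 24 for TPI. This assumes that the analysis tables not shown follow the two shells that are.

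**7. Labels side by side.**

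- Pairs: SAP 4.5.1, Protocol 10.2.2 and the shells' comparison rows agree with each other. Appendix 1's list differs from all of them.
- The MLSI (14.2.2.2), TPI (14.2.6.2) and adverse-event (14.3.1.1.1) shells have two Reference Product 1 columns and none for Reference Product 2.
- Table 14.1.3 heads its columns RDA 58, 77, 80 and 120. The arms in SAP 1.3 are RDA 38, 58, 36 and 166. Only 58 occurs in both, and it belongs to Test Product 2, not to the first column.

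**The case against.** The strongest reply is that the omission is deliberate. Both documents say openly that the primary objective has no comparisons, and Protocol 10.2.6 calls the study purely exploratory. The pairs of interest are the within-pair ones. A difference across pairs mixes silica type, silica level, STP and abrasivity, and the design does not claim to separate these. The standard error of any such difference is nearly recoverable from the printed table. All of this stands. It makes the point one of reporting, and it means the added rows should be descriptive and carry no claim about an ingredient.

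The list of outputs is an embedded spreadsheet, and the Section 16.1.9 SAS outputs named in Addendum 1 are not shown. The statement therefore covers the analysis text and visible shells only. Read literally, Appendix 1 would supply two of the four cross-pair differences, but no analysis section or shell row carries them.

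Four stronger readings are tempting and do not hold:

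- That Reference 2 vs Test 1 is the one missing link. It is so only if the protocol's expected order is observed.
- That tooth selection undermines the TPI p-values as well. TPI is scored on all gradable teeth, so only the lack of an untreated arm applies there.
- That starting Figures 14.2.3 and 14.2.4 at zero invites a test against zero. Change from baseline is zero at baseline by definition; this is a plotting convention.
- That the wrong contrasts would probably be programmed. Section 4.5.1, the protocol and the shell rows agree, and Appendix 1's own label list includes Reference Product 2, so the risk is low.

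**Conclusion.** The point holds as a reporting gap in the primary objective plus plain errors in the output instructions. For any observed order, one to three of the three adjacent steps have no planned difference. The reported per-arm half-width of 0.36 SD is not the precision of such a step, which is about 0.51 SD. These figures assume 30 evaluable per arm, near-balanced baselines and a common residual SD.

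A reader might infer that the ranking is biased, that a promised test was left out, or that information is lost. The documents do not support that: adjusted means and between-arm differences are unaffected, no primary comparison was promised, and the standard errors can be closely approximated. The unstated null for the per-arm p-values is minor. The Appendix 1 pairs and the column labels are wrong as written and need reconciling.

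**What to change.** **(a) Differences.** In SAP 4.4.1.2 and Table 14.2.2.2 add: *Week 8 adjusted mean differences with 95% CIs from the same ANCOVA will be shown for Reference 2 vs Test 1, Test 2 vs Test 1, Test 2 vs Reference 1 and Reference 2 vs Reference 1, without p-values, as descriptive support for the observed order and not as evidence on any single ingredient.* Addendum 1 was itself written after unblinding, so rows added at that point or later must be labelled post hoc.

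**(b) Per-arm p-values (minor).** Drop them, or state in 4.4.1.2, 4.6.1.2 and the table footnotes that the null is zero change and that they address neither rank nor product effect, because there is no untreated arm. For MLSI only, add the examiner's selection of teeth at baseline as a further reason.

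**(c) Labels.** In Appendix 1 replace the listed comparisons with Test 1 vs Reference 1 and Test 2 vs Reference 2, and list the descriptive rows from (a) separately. Change the second Reference Product 1 column to Reference Product 2 in the MLSI, TPI and adverse-event shells. Replace the Table 14.1.3 headings with this trial's four arms.

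**Cost.** Four extra estimates from a model already fitted, plus wording and label edits; no new data. The small downside is four more intervals unadjusted for multiplicity, which is why they carry no p-values and are labelled descriptive.

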Four of the anterior teeth will be selected for the purpose of stain assessment. Stain assessments will be made on the facial surfaces only as these surfaces are considered to be the most aesthetically important with respect to dental stain accumulation. The selection of 4 assessment teeth as opposed to 12, which is typically selected for this model, will allow teeth with a greater propensity for stain accumulation to be included in the total MLSI (A×I) scores thus enabling greater overall differences to be observed (if it exists) as teeth with low or zero stain scores will not be included in the overall total MLSI (A×I). Dental stain and plaque largely accumulate in the harder to reach interproximal areas, therefore in addition to analysis of the overall total MLSI (A×I) and overall TPI, the interproximal regions have also been given focus as an exploratory objective in this study. As most of the stain is removed from the body and gingival regions, it is expected that little change in the total gingival MLSI (A×I) and total body MLSI (A×I) will be observed, therefore, these variables are not being analysed in this study.

Plaque reductions are normally seen in the hard to reach areas of the mouth, therefore, using only 4 test teeth may not provide sufficient data to observe trends for plaque removal. Therefore, a full mouth evaluation will be conducted, and all gradable teeth will be assessed for TPI.

A single examiner will perform the dental stain and plaque assessments for all subjects at each assessment visit to avoid inter-examiner variability. To assess the repeatability of the stain and

GlaxoSmithKline Consumer Healthcare Confidential

Template Version Effective: 22-Jun-2017

Page 16 of 61

Document Name	09032d580fbc0768tpcoctol.pdf	Document Identifier	Effective Date
Type	Version		
eldo_clinicalellbc	0.0. DIFFERENT MESSER Version CURRENT	1090032d580fbc0768tpcoctol	14-Aug-2017 09:06:22

Potassium Nitrate / Sodium Fluoride

208078

Final 1.0 Clinical Protocol

plaque assessments repeat examinations will be performed by the dental examiner at each assessment visit.

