- Review Inclusion and Exclusion criteria. Pregnancy status will be confirmed verbally by the subject.
- Confirmation of subject eligibility.
- To prepare for study participation, instruct subjects on the use of the [Lifestyle Guidelines](#) and [Concomitant Treatment\(s\)](#) sections of the protocol.

6.1.2 Baseline MLSI Visit (Day 1) - Visit 2

Subjects will be admitted to the clinical site at least 24 hours following the Screening visit. Subjects will attend the study site having refrained from all oral hygiene procedures for at least 6 hours, and from eating and drinking for at least 2 hours (with the exception of water), prior to their scheduled visit.

The following procedures will be completed in the following order (where possible), and recorded in the CRF:

- Review changes in the subject's medical history including concomitant medication since Screening.
- Review of Inclusion Criteria 10, and Exclusion Criteria 12.b and e.
- Full OHT and OST examinations conducted by a medically qualified examiner. Record any changes since the Screening visit in the CRF.
- Confirm subject eligibility and continuance.
- Supervised brushing of the anterior teeth for 30 seconds using a wetted toothbrush, followed by flossing.
- Full MLSI stain assessment of the facial (maxillary and mandibular) teeth conducted by a qualified dental examiner.

GlaxoSmithKline Consumer Healthcare Confidential

Template Version Effective: 22-Jun-2017

Page 31 of 61

Document Name	003270B076tpctocol.pdf	Document Identifier	Effective Date
Type	Version		
eldo_clinicalelbc	0.0. DIFFERENT MESSAGING CURRENT	1090032d580fb904bc	14-Aug-2017 09:06:22

Potassium Nitrate / Sodium Fluoride

208078

Final 1.0 Clinical Protocol

- 4 eligible assessment teeth selected by a qualified dental examiner.
- Repeat full MLSI stain assessment of the 4 assessment teeth for selected subjects.
- Stratification (based on total MLSI score of the 4 facial surfaces of the 4 eligible assessment teeth).
- Unsupervised brushing with standard fluoride dentifrice.
- AEs and incidents. Assess symptoms by spontaneous reporting of adverse events and by asking the subjects to respond to a non-leading question such as “How do you feel?”

6.1.3 Baseline TPI Visit (Day 2) - Visit 3

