The purpose of this trial is to demonstrate the efficacy and safety of 5% Potassium Nitrate (KNO₃) / Sodium Fluoride (NaF) to treat the symptoms of extrinsic dental stain. Efficacy will be demonstrated through evaluating and comparing the extrinsic dental stain and plaque removal of an experimental low abrasivity 0.5% spherical silica dentifrice and a marketed low abrasivity 6% standard silica abrasive dentifrice, and an experimental moderate abrasivity 1% spherical silica / 5% sodium tripolyphosphate (STP) dentifrice and a marketed high abrasivity 16% standard abrasive silica / 5% STP dentifrice. Safety will be demonstrated through assessment of the incidence of adverse events (AEs).

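### The per-arm p-values for change in stain run above their 5% error rate, because the four teeth are chosen at the same Visit 2 scoring that serves as baseline

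*SAP*

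**What the plan says.** The primary model in SAP amendment 4.4.1.2 is "analysis of covariance (ANCOVA) with treatment as a fixed effect and baseline overall MLSI as a covariate". From it, "Adjusted means of all treatments will be provided together with their 95% Cis and p-values". SAP 4.6.1.2 repeats this for the exploratory variables: "the adjusted mean for each treatment group will be provided with 95% Cis and corresponding p-values". The shell of Table 14.2.2.2 has a p-value row for each arm, separate from the rows for the two product comparisons. By the text of 4.6.1.2, Tables 14.2.3.2 to 14.2.5.2 (interproximal, area and intensity scores) follow the same pattern.

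No null is written for the per-arm p-values. The only null in Protocol 10.2 concerns differences between treatments: "H0: there is no treatment difference versus the alternate hypothesis". For the ranking, Protocol 10.2.2 asks for adjusted means and intervals and does not mention a p-value per arm. The formal comparisons in SAP 4.5.1 are "treatment differences between groups (Test Product 1 vs Reference Product 1 and Test Product 2 vs Reference Product 2), 95% Cis and p-values".

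On the teeth, the Schedule of Activities (footnote 2) has all 12 anterior teeth scored at Visit 2. The next step in Protocol 6.1.2 is "4 eligible assessment teeth selected by a qualified dental examiner". Protocol 1.2.2 explains that taking four teeth instead of 12 "will allow teeth with a greater propensity for stain accumulation to be included", and that teeth scoring low or zero are kept out of the total. SAP 1.1 leaves the choice to the examiner's judgement. SAP 3.1 defines baseline as the last non-missing pre-dose assessment, which for stain is the Visit 2 scoring. Repeat scorings are kept out of efficacy (SAP 4.8).

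**The concern.** A tooth can score high at Visit 2 because it carries more stain or because that day's score erred upwards. Choosing teeth for high scores picks up both. At later visits the error is drawn afresh, so the same teeth score lower on average with no change in stain. Because the selecting score is also the baseline, the whole drop enters the change from baseline, and it does so in all four arms.

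A test of each arm's change against zero would then reject more than 5% of the time for a paste that does nothing, almost always in the favourable direction. No untreated arm shows how much of the fall is artefact. The stain tables would hold 4 endpoints × 3 visits × 4 arms = 48 such p-values, all resting on the same Visit 2 scoring.

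**Working it through.** **1. The plan's own figures.** 120 evaluable / 4 arms = 30 per arm; 124 randomized to 120 evaluable is a loss of 4/124 = 3.2%. The power inputs are redacted, and no error rate is stated for the per-arm p-values, so there is none to reproduce. Two-sided 0.05 is assumed, from the 95% intervals.

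**2. Size of the shift in a simple model.** For normal tooth scores with test-retest reliability r, the four highest of 12 lie on average 1.02 SD above the subject's mean. The expected fall at the next scoring is (1 − r) × 1.02 SD:
- r = 0.95: 0.05 × 1.02 = 0.05 SD
- r = 0.75: 0.25 × 1.02 = 0.26 SD
- r = 0.40: 0.60 × 1.02 = 0.61 SD

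**3. Why the covariate does not help.** The adjusted mean of arm k is (mean change in k) − b × (baseline mean in k − overall baseline mean). With equal arms the second term averages to zero, so the adjusted means average to the overall raw change. The adjustment is made to a baseline mean that the selection has already raised, and the shift stays in full. A shift common to all arms cancels in any difference between two arms.

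**4. Simulation of the planned ANCOVA with no true change.**
- From the documents: 4 arms × 30; 12 teeth × 4 sites; area and intensity each 0-3; model with treatment and baseline.
- Assumed: the four highest-scoring teeth are kept; median selected total of 15 (the stratum boundary); latent variances of 0.3 (subject), 0.3 (tooth) and 0.4 (site); scoring error and day-to-day variation varied to span weighted kappa from about 0.45 to 0.92. There were 1,000 trials per setting.

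| Weighted kappa, about | One arm p < 0.05 |
|---|---|
| 0.90 | 8-21% |
| 0.82 | 12-33% |
| 0.75 | 15-47% |
| 0.65 | 34-73% |
| 0.47 | 71-94% |

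The ranges reflect the day-to-day variation assumed. SAP 4.8 calls kappa above 0.75 excellent and 0.4 to 0.75 fair to good.

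At kappa about 0.75 the spurious change in the four-tooth total runs from −2.04 (on 21.6) to −4.44 (on 23.6). Divided by 16 sites, that is −0.13 to −0.28 on the planned per-site scale, against a baseline of about 1.3 to 1.5.

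Hand check of the −2.04 setting: the SD of change is 6.2, so SE = 6.2/√30 = 1.13 and 2.04/1.13 = 1.80. P(Z > 1.96 − 1.80) is about 0.44, close to the simulated 47%.

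**5. Varying the selection.** At kappa about 0.75 with intermediate day-to-day variation, top-4-of-12 selection gives 24%. Against that:
- score plus judgement noise: 19-23%
- 10, 8 or 6 gradable teeth: 21%, 13%, 9%
- only 4 gradable teeth: 4.7%
- larger true tooth-to-tooth spread (kappa about 0.80): 11%
- teeth chosen on an independent earlier scoring: 4.6%
- teeth chosen without regard to score: 5.7%

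The last two bring the rate back to about 5%, so the excess comes from selecting on the baseline score.

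**6. Between-arm test.** 3-7% in all settings, about nominal.

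Only the overall area × intensity score was simulated. The other three stain endpoints use the same teeth and scoring, so they share the mechanism, but their rates were not computed.

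**The case against.** The written selection rule is examiner judgement, limited by the tooth exclusions; nothing says the highest four scores. That stands: selection on the Visit 2 scores is inferred from the order of steps and the stated aim. Judgement noise lowers the rate only to 19-23% at kappa about 0.75.

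The documents give no repeatability, SD or tooth-to-tooth spread, and inclusion criterion 8 requires only four gradable teeth. That stands too, and it is why the result is a range.

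The strongest argument is that no alpha, null or decision rule is attached to these p-values. The primary aim is ranking, the formal tests are between products, and the study is an exploratory proof of principle. This limits the harm but does not make the printed p-values correct.

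Two stronger readings are tempting and are not supported:
- A reader might infer that the plaque tables share the fault, because entry requires a pre-brushing TPI of at least 2.0 on the score used as baseline. But no teeth are selected for TPI; all gradable teeth are scored, and the only selection is on a whole-mouth mean. With 30 per arm, a normal score and a one-sample t-test, the per-arm rate is 5.6%, 6.1% and 9.3% if 5%, 10% and 20% of subjects fail the cut-off at an assumed reliability of 0.8. At reliability 0.6 it is 5.7%, 7.6% and 14%. Unless many fail, this is near nominal.
- SAP Section 1 states the purpose as "to demonstrate the efficacy and safety of 5% Potassium Nitrate", which all four pastes contain. A reader might infer that only the within-arm tests could support that purpose. The next sentence says efficacy is shown by evaluating and comparing the test and marketed pastes, and nothing says the per-arm p-values will be offered as proof.

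**Conclusion.** The point holds for the stain endpoints. If the per-arm p-values test change against zero, their false-positive rate is above 5% whenever more than four teeth are gradable and the choice leans on the Visit 2 scores. Under top-4-of-12 selection the rate is about 8-21% at kappa about 0.9 and 15-47% at about 0.75. The direction follows from the design; the size depends on the assumed repeatability and spread.

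It would be wrong to conclude that the trial's main results are biased. The shift is common to the randomized arms, so the rank order of adjusted means and the comparisons of Test Product 1 with Reference Product 1 and Test Product 2 with Reference Product 2 are unaffected. What is at fault is a set of p-values that no stated objective needs.

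**What to change.** In the SAP:
- Delete the per-arm p-value row from Tables 14.2.2.2 to 14.2.5.2, and the matching words in 4.4.1.2 and, for the stain variables, 4.6.1.2.
- In these tables keep p-values only for Test Product 1 vs Reference Product 1 and Test Product 2 vs Reference Product 2.
- Keep the per-arm adjusted means and 95% intervals for the ranking, but footnote them to say that within-arm change includes regression to the mean and is not evidence of a product effect. An interval that excludes zero is the same test in another form, so the footnote is needed. Put it also on Figure 14.2.3 in Addendum 1, which plots these intervals from a zero baseline.

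The cost is one table row and a footnote; within-arm significance can no longer be reported.

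Moving tooth selection to Visit 1 is not recommended. Protocol 6.1.1 describes only a visual stain assessment there, without the brushing, flossing and hygiene abstention that precede the Visit 2 scoring. Inclusion criterion 10 would still select subjects on their Visit 2 stain.
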